For this study, based on our expertise and on the rules of thumb mentioned above, we approximated that a minimum of 250 patients with AI are needed to identify generalizable features. With an incidence of AI of 5% for colon anastomosis and 8% for colorectal anastomosis, that means that a minimum of 5000 and 3125 patients are required for training for each population (colocolic and colo-rectal anastomosis, respectively). For satisfactory evaluation of calibration at external validation, we estimate that another 2000 and 1250 patients per cohort (thus, approximately 100 with AI per cohort) will be required. Thus, in total, we estimate that **7000 (colocolic anastomosis) and 4375 (colorectal anastomosis) patients** are necessary to reach at a satisfying model. More data will likely lead to greater performance and better calibration.

Predictive Modeling

A KNN imputer will be co-trained to impute any missing data that may occur in future application of the model. If there is missing data in the training set, it will be imputed using said KNN imputer. [39] Features or patients with a missingness greater than 25% will be excluded. Data will be standardized and one-hot-encoded. In case of major class imbalance – which is expected for the abovementioned endpoint – random upsampling or synthetic minority oversampling (SMOTE) will be applied to the training set. [40, 41] All features will at first be given to the model for training. If needed, we will employ recursive feature elimination (RFE) to choose input features on the training data. [42]

We will trial the following algorithms for binary classification: Generalized linear model (GLM), generalized additive model (GAM), stochastic gradient boosting machine (GBM), naïve Bayes classifier, artificial neural network, support vector machine (SVM), and random forest. Each model will be fully trained and hyperparameter tuned where applicable. The final model will be selected based upon (AUC), sensitivity, and specificity, as well as calibration metrics on the resampled training performance. Training will happen in repeated 5-fold cross-validation with 10 repeats.

The one final model will then be examined on the external validation data only once. Ninety-five percent confidence intervals for external validation metrics will be derived using the bootstrap.

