The threshold for binary classification will either be identified on the training data alone using the AUC-based “closest-to-(0,1)-criterion” or Youden’s index to optimize both sensitivity and specificity or will be optimized on the training set based on clinical significance (rule-out model). The analyses will be carried out in R Version 3.6.2. [43] or Python.

Evaluation

The efficacy of classification models can be approximately evaluated along two dimensions: Model discrimination and calibration. [44] The term *discrimination* denotes the ability of a prediction model to correctly classify whether a certain patient is going to or is not going to suffer a certain outcome. Thus, discrimination describes the accuracy of a binary prediction – yes or no. *Calibration*, on the other hand, defines the degree to which a model’s predicted probabilities (ranging from 0% to 100%) correspond to the observed incidence of the binary endpoint (true posterior). Many publications do not report calibration metrics, although these are of central importance, as a well-calibrated predicted probability (e.g. your predicted probability of experiencing a complication is 18%) is often much more valued to clinicians – and patients! – than a binary prediction (e.g. you are likely not going to experience a complication). [44]

Resampled training performance as well as performance on the external validation set will be examined for discrimination and calibration. In terms of discrimination, we will assess AUC, accuracy, sensitivity, specificity, positive predictive value (PPV), negative predictive value (NPV), and F1 Score. In terms of calibration, we will assess the Brier score, expected-observed (E/O) ratio, calibration slope and intercept, the Hosmer-Lemeshow goodness-of-fit test, as well as visual inspection of calibration plots for both datasets, which will also be included in the publication.

Interpretability

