The degree and choice of methods for interpretability will rely upon on the final chosen algorithm. Some algorithms can natively give explanations as to which factors affect the outcome in what way. Thus, in case e.g., a GLM, GAM, or naïve Bayes classifier is chosen, the parameters / partial dependence values will be provided. For simple decision trees, diagrams of the decision-making process can be given. Other models with higher degrees of complexity, such as neural networks or stochastic gradient boosting machines cannot natively provide such explanations. In that case, we will provide both AUC-based variable importance as well as model-agnostic local interpretations of variable importance using the LIME principle. [45]

Expected Results

We foresee arriving to a generalizable model based on multicenter international data that is likely to predict AI consistently with an AUC of at least 0.70 (more realistically 0.8 or greater) and that is well-calibrated. [44] A web-based prediction tool will also be designed for each of the two models applying the *shiny* [46] environment, much likened to e.g., <https://neurosurgery.shinyapps.io/impairment>. This web-based app will be accessible for free on any internet-capable device (mobile or desktop), and should be stable on most devices due to the server-based computing. The costs for maintaining the server will be carried by the main investigators.

The assembled data will be saved for 10 years by the sponsor. The large dataset will be available to further analysis and will be given to any of the participating centers at request and after approval by all other centers. The goal is to facilitate other analyses using the collected dataset. If any other analyses reach publication, all contributors will be included as co-authors and all co-authors will have the opportunity to review said manuscript beforehand. Any contributing study center has the right to veto publication of any subsequent analyses containing their own data.

Acknowledgement: The study idea and the study protocol were developed together with [name] (Machine Intelligence in Clinical Neuroscience (MICN) Laboratory, Clinical Neuroscience Center, University Hospital Zurich).

References

1. Lee, S.W., D. Gregory, and C.L. Cool, Clinical and economic burden of colorectal and bariatric anastomotic leaks. *Surg Endosc*, 2019.

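### Upsampling or SMOTE is applied to the training set, and the final model is chosen by cross-validating that set, with no rule that held-out folds stay unbalanced

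*Protocol*

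**What the plan says.** All places are in the protocol.

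- *Predictive Modeling* expects major class imbalance for the endpoint and says that "random upsampling or synthetic minority oversampling (SMOTE) will be applied to the training set". No target ratio is given.
- *Sample Size* shows what training refers to: "a minimum of 5000 and 3125 patients are required for training for each population". The external cohorts of 2000 and 1250 patients are counted separately.
- *Predictive Modeling* continues: "The final model will be selected based upon (AUC), sensitivity, and specificity, as well as calibration metrics on the resampled training performance". The resampling scheme follows: "Training will happen in repeated 5-fold cross-validation with 10 repeats".
- On the external data: "The one final model will then be examined on the external validation data only once".
- On the cut-off: "The threshold for binary classification will either be identified on the training data alone", or tuned on the training set for a rule-out purpose.
- *Evaluation* adds: "Resampled training performance as well as performance on the external validation set will be examined for discrimination and calibration".
- *Expected Results* anticipates a model that "is likely to predict AI consistently with an AUC of at least 0.70 (more realistically 0.8 or greater) and that is well-calibrated".

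No sentence says whether balancing is redone within each fold, or whether held-out folds keep real patients at the real incidence.

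**The concern.** Cross-validation is informative only if the held-out part resembles new patients. If the whole development cohort is balanced and then split, two things go wrong.

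1. A held-out leak patient has a duplicate (upsampling) or an interpolated relative (SMOTE) in the data used for fitting. Learners that can memorise are rewarded for it.
2. The held-out folds carry the artificial incidence, so calibration is judged against the wrong target.

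These cross-validated figures choose the algorithm and are reported as training performance. They may also set the cut-off. Because only one model goes to external validation, a poor choice would show up there, but the plan has no route for replacing it.

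**Working it through.** **Inputs from the protocol.** 250 leak cases per model; incidence 5% and 8%; 5 folds, 10 repeats. The training sizes reproduce: 250/0.05 = 5000 and 250/0.08 = 3125.

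**Assumption.** The balancing ratio is not stated, so 1:1, 1:2 and 1:4 (leak : no leak) are shown.

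**Step 1: rows per leak patient if balanced before splitting.** Patients without a leak: 5000 − 250 = 4750 and 3125 − 250 = 2875.
- 1:1: 4750/250 = 19 (PANIC-C) and 2875/250 = 11.5 (PANIC-R).
- 1:4: (4750/4)/250 = 4.75 and (2875/4)/250 ≈ 2.9.

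**Step 2: chance that a held-out leak row has no copy in the training folds.** For upsampling with replacement, with d rows added and 4/5 of rows in the training folds:

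[250·(1 − 0.8/250)^d + d·0.2·(1 − 0.8/250)^(d−1)] / (250 + d)

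The first term covers the 250 real rows and the second the d added rows.

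| Ratio | d, PANIC-C | no copy | d, PANIC-R | no copy |
|---|---|---|---|---|
| 1:1 | 4500 | 1.3e-7 | 2625 | 6.0e-5 |
| 1:2 | 2125 | 3.1e-4 | 1187.5 | 0.0075 |
| 1:4 | 937.5 | 0.018 | 468.75 | 0.107 |

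So over 99.9% of held-out leak rows have an identical copy at 1:1, and 98% and 89% at 1:4. With SMOTE the relative is interpolated, not identical.

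**Step 3: incidence in the held-out folds.** 1/(1+1) = 50% at 1:1 and 1/(1+4) = 20% at 1:4, against 5% and 8% in patients.

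**Step 4: effect on AUC.** The signal strength is assumed in both simulations.

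*Simulation A:* 30 independent features, 10 informative, true AUC 0.70, 1:1 ratio, two datasets per setting, 40,000 new patients. Ranges cover both cohorts and both balancing methods.

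| Learner | Balanced first | Inside folds | New patients |
|---|---|---|---|
| GLM | 0.74–0.77 | 0.70–0.71 | 0.67–0.68 |
| Random forest | 0.99–1.00 | 0.62–0.64 | 0.61–0.63 |
| Boosting | 0.99–1.00 | 0.61–0.63 | 0.59–0.62 |

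*Simulation B:* 35 features, best possible AUC 0.74 (linear truth) or 0.81 (nonlinear), 20,000 new patients, one repeat of 5 folds. The mean gap between cross-validated and new-patient AUC over the candidates was 0.14–0.28 when balanced first and 0.014–0.023 inside the folds.

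**Step 5: effect on calibration (GLM, simulation B, upsampling).** Expected/observed ratio:

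| Ratio | Balanced first (both models) | Inside folds and new patients, PANIC-C | Same, PANIC-R |
|---|---|---|---|
| 1:1 | 1.00 | 8.0 | 5.1 |
| 1:2 | 1.00 | 5.5 | 3.5 |
| 1:4 | 1.00 | 3.4–3.5 | 2.3 |

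At 1:1 the mean predicted risk in new patients is about 8.0 × 5% = 40% and 5.1 × 8% = 41%.

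**Step 6: effect on the model chosen (simulation B).**
- Selection on AUC alone, linear truth: balanced first, a full-depth forest or deep boosting won 40 of 40 runs, with cross-validated AUC 0.96–1.00 and new-patient AUC 0.64–0.67. Inside folds the chosen model had 0.72.
- Equal-weight ranks of AUC, sensitivity plus specificity, Brier score, E/O and slope (weights assumed): with upsampling, new-patient AUC was 0.65–0.70 balanced first and 0.71–0.75 inside folds. With SMOTE it was 0.66–0.69 and 0.66–0.70, practically no difference.

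**Step 7: cut-off (simulation B).** This assumes a Youden cut-off taken from the cross-validated predictions. A full-depth forest then shows sensitivity 0.98–1.00 in leaked folds but 0.00–0.02 in new patients; with the in-fold cut-off it reaches 0.51–0.61. For the GLM the source of the cut-off hardly matters (0.62 against 0.63).

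**The case against.** The strongest reply is that the protocol never says balancing comes before splitting. The section is not in order of execution: cross-validation is described after model selection. Since training takes place in folds, the training set could mean the part being fitted, and a team may leave such detail to an analysis plan or code. This stands in part. In-fold balancing is compatible with the text, and a reader who infers that the protocol prescribes leakage goes too far. But *Sample Size*, *Predictive Modeling* and *Evaluation* set training against the external data, and none uses the term for part of a fold. The rule as written therefore points to the whole cohort.

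Second, the external data are untouched, and both sets of results are reported. This stands: one might infer that the external performance is biased, and it is not. A cross-validated AUC near 1.00 would also be a visible warning.

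Third, the harm to model choice rests on assumptions. This stands too. The 40-of-40 result uses AUC alone, whereas the protocol names several criteria without weights. SMOTE under a multi-metric rule shows almost no AUC gain from the fix. SVM and neural network were not simulated, and the forest and boosting settings were extremes. Inside the folds the metrics conflict (PANIC-C, 1:1: GLM AUC 0.73 with E/O 8.0; full-depth forest 0.66 with 1.4), so it does not follow that the GLM would or should win.

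Fourth, the miscalibration comes from balancing itself. Correct; leaked folds only hide it.

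**Conclusion.** The point holds as a defect of wording with real consequences if the wording is followed. The cross-validated discrimination and calibration would then be unreliable both as selection criteria and as reported training performance. The duplication and the shift in incidence follow by arithmetic once a ratio is assumed. The inflated AUC of flexible learners appeared under two different data models, though its exact size depends on the assumed signal. For a GLM at 1:1, an E/O near 1.0 would conceal overprediction of roughly 8-fold (PANIC-C) and 5-fold (PANIC-R).

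The documents do not support three stronger conclusions: that balancing is certain to precede splitting, that the external estimate is compromised, or that the wrong model will necessarily be chosen. The loss of sensitivity applies only if the cut-off comes from the same leaked predictions; the rule-out option was not simulated. Severity is low to moderate.

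**What to change.** Add to *Predictive Modeling*:

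*Any upsampling or SMOTE is applied only to the training part of each cross-validation fold; held-out folds keep their original patients and natural incidence for all selection and reported metrics, including calibration, and for setting the threshold.*

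The cost is one sentence and repeating the balancing step in each of the 5 × 10 = 50 training parts. No extra data are needed. If the team already works this way, the sentence only records it. Nested hyperparameter tuning is not asked for: it would require inner tuning within each of the 50 fits, and no benefit was shown here.

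The downside is that training figures will look less favourable. The miscalibration caused by balancing will become visible at selection, but it is not removed and still has to be dealt with.
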